9.5.1.4.2 IRRECIST AFTER INITIAL RADIOLOGIC PROGRESSION

Since pembrolizumab, like other immunotherapeutic agents, may produce antitumor effects after an initial increase in tumor burden, standard RECIST criteria may not provide a complete response assessment of its efficacy. irRECIST is RECIST 1.1 adapted as described below to account for the unique tumor response seen with immunotherapeutic drugs. irRECIST will be used by site investigator/local radiology review to assess tumor response and progression, and make treatment decisions. This data will be collected in the clinical database. Treatment efficacy based on irRECIST as assessed by central imaging vendor review will be evaluated retrospectively.

The key changes for irRECIST from RECIST v1.1 is the ability to continue treatment, if clinically stable, until a repeat imaging scan \geq 4 weeks after the first radiologic evidence of PD confirms progressive disease. Therefore, in addition to radiographic assessment of tumor response or progression, irRECIST (see [Appendix 4](#)) takes into account the clinical condition/stability of subjects ([Table 6](#)).

Clinically stable is defined by the following criteria:

- Absence of signs and symptoms (including worsening of laboratory values) indicating disease progression
- No decline in ECOG performance status
- Absence of rapid progression of disease
- Absence of progressive tumor(s) at critical anatomical sites (eg, cord compression) requiring urgent alternative medical intervention
- No requirements for intensified management, including increased analgesia, radiation, or other palliative care

Table 6 Imaging and Treatment After First Radiologic Evidence of Progressive Disease

	Clinically Stable		Clinically Unstable	
	Imaging	Treatment	Imaging	Treatment
1 st radiologic evidence of PD by RECIST 1.1	Repeat imaging at ≥ 4 weeks at site to confirm PD	May continue study treatment at the local site investigator's discretion while awaiting confirmatory tumor imaging by site by irRECIST	Repeat imaging at ≥ 4 weeks to confirm PD per physician discretion only	Discontinue treatment
Repeat tumor imaging confirms PD by irRECIST at the local site	No additional imaging required	Discontinue treatment (exception is possible upon consultation with sponsor)	No additional imaging required	N/A

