Appendix 4 Immune-related Response Evaluation Criteria in Solid Tumors (irRECIST)

Investigators should follow the guidelines provided here, which are an adaptation of RECIST 1.1 and immune-related response criteria (irRC). The following guide represents a summary of irRECIST and is meant to help investigators in providing more objective and reproducible immune therapy-related tumor response assessments in solid tumors.

The key changes for irRECIST are:

- For this study, similar to that allowed for RECIST 1.1, irRECIST allows the site to select up to 5 target lesions at baseline, 2 per organ, if clinically relevant via CT/MRI scans or by electronic calipers for skin lesions. The ability to continue treatment, if clinically stable, until repeat imaging scans \geq 4 weeks later (in most cases at the next scanning time point) to confirm immune-related progressive disease (irPD)

irRECIST Lexicon	
1. Baseline Assessments	
Measurable (Target) Lesions	Measurable lesions must be accurately measured in at least 1 dimension with a minimum size of: 
• 10 mm in the longest diameter (LD_i) by CT or MRI scan (or no less than double the slice thickness) for non-nodal lesions and \geq15 mm in short axis (SD_i) for nodal lesions• 10 mm in LD_i for clinical lesions (must be measured using electronic calipers)• Identify up to 5 lesions, not more than 2 from 1 organ system. Lymph nodes are considered 1 organ system• Likely to be reproducible across all time points• Representative of tumor burden• May include lesions in previously irradiated areas ONLY if there is demonstrated progression in that lesion after irradiation• Sum of diameters (SOD) of all target lesions including nodal and non-nodal are reported as baseline SOD which is used for assessing tumor response at follow-up time points
Bone Lesions	Regardless of the imaging modality, blastic bone lesions will not be selected as target lesions. Lytic or mixed lytic-blastic lesions with a measurable soft tissue component \geq 10 mm can be selected as target lesions.
Cystic and Necrotic Lesions as Target Lesions	Lesions that are partially cystic or necrotic can be selected as target lesions. The longest diameter of such a lesion will be added to the SOD of all target lesions at baseline. If other lesions with a nonliquid/nonnecrotic component are present, those should be preferred.

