	Clinically Stable		Clinically Unstable																						
	Imaging	Treatment	Imaging	Treatment																					
1st radiologic evidence of PD by RECIST 1.1	Repeat imaging at ≥ 4 weeks (next TA time point) to confirm PD	May continue study treatment at the local site investigator's discretion while awaiting confirmatory tumor imaging by site by irRECIST	Repeat imaging at ≥ 4 weeks to confirm PD per physician discretion only	Discontinue treatment																					
Subsequent tumor imaging confirms PD by irRECIST at the local site	No additional imaging required	Discontinue treatment (exception is possible upon consultation with sponsor)	No additional imaging required	N/A																					
Subsequent tumor imaging shows SD, PR, or CR by irRECIST at the local site	Continue regularly scheduled imaging assessments	Continue study treatment at the Investigator's discretion	Continue regularly scheduled imaging assessments	May restart study treatment if condition has improved and/or clinically stable per investigator's discretion. Next tumor image should occur according to the every 9 weeks \pm 1 week imaging schedule																					

	irPD if they are clinically stable as defined by the following criteria: 
• Absence of signs and symptoms (including worsening of laboratory values) indicating disease progression• No decline in ECOG performance status• Absence of rapid progression of disease• Absence of progressive tumor at critical anatomical sites (eg, cord compression) requiring urgent alternative medical intervention If irPD is confirmed and the subject is experiencing extraordinary clinical benefit, site must contact the sponsor to discuss continuing treatment.
irNE	Used in exceptional cases where insufficient data exists due to poor quality of scans or missed scans or procedure.

In determining whether or not the tumor burden has increased or decreased, local study site investigators should consider all target lesions as well as non-target lesions. Subjects that are deemed clinically unstable are not required to have repeat tumor imaging for confirmation.

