- For a clinically stable subject with first radiologic evidence of progressive disease by RECIST 1.1 (ie, unconfirmed progression of disease), it is at the discretion of the site investigator to continue treating the subject with the assigned treatment per protocol until progression of disease is confirmed at least 28 days from the date of the scan first suggesting PD. If radiologic progression is confirmed by subsequent scan then the subject will be discontinued from study treatment. If radiologic progression is not confirmed by irRECIST per the site, then the subjects may continue on treatment and follow the regular imaging schedule intervals until progression is confirmed at a later timepoint by the site.
 - o NOTE: If a subject has confirmed radiographic progression (ie, 2 scans at least 4 weeks apart demonstrating progressive disease) per irRECIST, but the subject is achieving a clinically meaningful benefit, and there is no further increase in the tumor burden at the confirmatory tumor imaging, an exception to continue treatment may be considered following consultation with the Sponsor. In this case, if treatment is continued, tumor imaging should continue to be performed following the intervals as outlined in sections 6.0 Study Flowchart and be submitted to the central imaging vendor. Note: As of Protocol Amendment 05, tumor assessment scans will no longer be sent to the central imaging laboratory.
- Any subject deemed clinically unstable should be discontinued from study treatment at 1st radiologic evidence of PD and is not required to have repeat imaging for PD confirmation.
- In subjects who discontinue study therapy without documented disease progression, every effort should be made to continue monitoring their disease status by tumor imaging using the same imaging schedule used while on treatment (every 9 weeks \pm 1 week in Year 1, and every 9 to 12 weeks \pm 1 week thereafter according to standard of care), until (1) the start of new anti-cancer treatment, (2) disease progression (3) death, or (4) the end of the study, whichever occurs first.

Derivation of irRECIST overall responses			
Measurable response	Nonmeasureable response		
Target Lesions (% change in SOD)*	Nontarget Lesions Status	New Lesions Status	Overall Response (irRECIST)
↓100	Absent	Absent	irCR [¥]
↓100	Present/NE	Absent	irPR [¥]
↓≥30	Present/Absent/NE	Absent	irPR [¥]
↓<30 to <20↑	Present/Absent/NE	Absent	irSD
↓100 ↓≥30 ↓<30 to <20↑ NE	Present/Absent/NE	Present	irPD [¥]

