Definition of BOR by irRECIST

- Investigator Review

Subjects who experience PD defined by RECIST1.1 will have a confirmation scan at least 4 weeks apart to confirm PD (irPD). Subjects may continue receiving study treatment while waiting for confirmation of irPD if they are clinically stable. If a subject discontinued study treatment without confirmation of irPD, the subject will be counted as irPD.

Tumor assessments after any new anti-cancer therapy, including the palliative radiotherapy, will be deleted in defining BOR. The overall time point tumor response data collected via both the CRF of the irRECIST and the CRF of the RECIST 1.1 will be used. Simply add prefix 'ir' to CR/PR/SD/PD/NE from RECIST 1.1 and follow the definition of BOR per RECIST 1.1 to define BOR per irRECIST (irCR/irPR/irSD/irPD/irNE). Table 2 describes the scenarios of PD by RECIST 1.1 followed by different confirmation scans.

Table 2. BOR by irRECIST for Scenarios with PD (defined by RECIST 1.1) Followed by Subsequent Scans

Timepoint 1 Overall Response	Timepoint 2 (\geq 4 weeks since Timepoint 1) Overall Response	BOR by irRECIST
PD	CR ^a	If subject has been followed for \geq 4 weeks and CR is confirmed, BOR is irCR. If CR not confirmed, then follow same rule as BOR by definition of RECIST 1.1.
PD	PR ^a	If subject has been followed for \geq 4 weeks and PR is confirmed, BOR is irPR. If PR not confirmed, then follow same rule as BOR by definition of RECIST 1.1.
PD	SD ^b	irSD
PD	PD ^c	irPD
PD	NE	irPD
PD		irPD, if no confirmation scan.

^a The subject should be followed for \geq 4 weeks to confirm the CR/PR.

^b The subject is on the study treatment and followed for further tumor assessments.

^c PD is confirmed. The subjects should be discontinued from the study treatment, and no further tumor response assessments will be performed.

Other exploratory endpoints using irRECIST: ORR, PFS, DOR, CBR and DCR will be derived similarly as those using RECIST1.1; but the derivation will be based on irCR, irPR, irSD and irNE instead of CR, PR, SD and NE.

- Independent Imaging Review

BOR by irRECIST for IIR data will follow the same principle as above except tumor assessments by mRECIST 1.1(modified RECIST 1.1) criteria for the time points up to PD are used.

Censoring rule for OS

Subjects who are lost to follow-up or withdrawal from study will be censored at the last date the subject was known to be alive, and subjects who remained alive will be censored at the time of data cutoff.

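### Protocol Section 9.5.1.4.2 has a fifth criterion for clinical stability that Appendix 4 omits, so some subjects at first progression get opposite stop-or-continue instructions, which can change exploratory irRECIST outcomes

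*Protocol*

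**What the plan says.** Protocol Section 9.5.1.4.2 defines clinically stable by five criteria. The fifth is "No requirements for intensified management, including increased analgesia, radiation, or other palliative care". The section also refers the reader to Appendix 4 for irRECIST.

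Appendix 4 opens with "Investigators should follow the guidelines provided here, which are an adaptation of RECIST 1.1". In its irPD entry it permits treatment while awaiting confirmation of "irPD if they are clinically stable as defined by the following criteria". Four criteria follow, and the list ends at "Absence of progressive tumor at critical anatomical sites (eg, cord compression) requiring urgent alternative medical intervention". It says nothing about analgesia, radiation or palliative care.

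Both places attach the same consequence to the term. A stable subject may continue after first radiologic PD at the investigator's discretion. For the rest, Appendix 4 says "Any subject deemed clinically unstable should be discontinued from study treatment", and Section 9.5.1.4.2 says the same. The synopsis uses the term without defining it.

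SAP Section 8 (definition of BOR by irRECIST) adds: "If a subject discontinued study treatment without confirmation of irPD, the subject will be counted as irPD". SAP Table 2 classifies a PD that is followed by a further scan according to that scan.

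**The concern.** The term decides whether a subject stays on study drug after first progression. Both lists are current text, both are addressed to the site, and neither is given precedence. For a subject who falls between them, treatment depends on which page the investigator opens.

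There is also a limited analysis consequence. The irRECIST rules reward having a further scan on continued treatment, so a difference in who continues can become a difference in exploratory BOR, ORR, PFS and CBR that reflects site reading as well as tumour behaviour.

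**Working it through.** No sample size, power or alpha figure is involved. The check sets the two lists side by side and traces the subjects who fall between them.

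**1. The two lists (paraphrased)**

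| Criterion | Section 9.5.1.4.2 | Appendix 4 |
|---|---|---|
| No signs, symptoms or laboratory worsening pointing to progression | yes | yes |
| ECOG status not worse | yes | yes |
| Disease not progressing rapidly | yes | yes |
| No progressing tumour at a critical site needing urgent other treatment | yes | yes |
| No need for intensified management | yes | absent |
| Total | 5 | 4 |

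The lists diverge only for a subject who meets the first four criteria and fails the fifth.

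**2. Such a subject who needs more analgesia**

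- Under Section 9.5.1.4.2 the subject is unstable and is to be discontinued. With no confirmatory scan, the SAP counts irPD and dates it at the RECIST 1.1 PD.
- Under Appendix 4 the subject is stable and may continue. By SAP Table 2, PD followed by SD is irSD, and PD followed by a confirmed PR or CR is irPR or irCR. The progression date for irRECIST PFS then moves to the first irPD after that.
- Illustration: PD at Week 9, PR at Week 13 (9 + 4), PR again at Week 18 (13 + 5, so the 4-week confirmation interval is met). The result is irPR if the subject continued and was scanned, and irPD if treatment stopped without a rescan.

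This trace takes first PD at the first post-baseline scan. A subject with an earlier response or qualifying stable disease would already have a better BOR under either list.

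**3. Such a subject who needs radiation**

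- The stop-or-continue instruction still differs between the lists.
- Protocol Section 9.4.6.3 separately prohibits radiation on treatment, apart from case-by-case exceptions after consulting the sponsor.
- SAP Section 8 deletes assessments after palliative radiotherapy when deriving irRECIST BOR. If radiation is given after first PD and before the next scan, no later scan counts. PD is then unconfirmed, and BOR stays irPD under either list.

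**4. Primary endpoint**

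For BOR by RECIST 1.1, SAP Section 8 deletes assessments after PD. Continuing past first PD cannot alter primary ORR.

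**5. Effect of one reclassified subject on an irRECIST rate**

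- All evaluable subjects: 1/165 = 0.006, about 0.6 percentage points.
- Stratum 2: 1/100 = 0.010, or 1.0 percentage point.

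**The case against.** The strongest reply is that the lists rarely disagree in practice. Both require "Absence of signs and symptoms (including worsening of laboratory values) indicating disease progression" and no ECOG decline. A subject with radiologic PD and new tumour pain may fail that shared criterion and be unstable under both. This narrows the gap but does not close it: Section 9.5.1.4.2 lists intensified management as a separate condition, and an investigator may not attribute the pain to progression.

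A second reply is that Appendix 4 describes itself as a summary meant to help investigators, so the body governs. The documents do not say so; the appendix also tells investigators to follow it. The amendment history records an update to these criteria under Amendment 04 with only Section 9.5.1.4.2 listed as affected. That may explain how the lists came apart, but it sets no precedence.

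A third reply is that outcomes need not differ. This stands. Continuing is discretionary even for a stable subject, whose PD may then be confirmed. An unstable subject may be rescanned at the physician's discretion and may restart treatment if the condition improves. The right word is can, not will.

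A reader might infer that the mismatch also changes the irRECIST result of a subject who receives palliative radiation. The SAP's deletion rule does not support that, as step 3 shows.

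Timing is no answer. Under Amendment 05 subjects were still on treatment, with the last expected to complete by November 2020, so the rule remained in use.

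**Conclusion.** The protocol contradicts itself on an operative rule. For subjects at first radiologic PD who need intensified management and meet the four shared criteria, Section 9.5.1.4.2 says discontinue and Appendix 4 says treatment may continue. Where the need is for more analgesia, exploratory irRECIST BOR, ORR, PFS and CBR can also differ, by about 0.6 points per reclassified subject for a rate in all 165 evaluable subjects, or 1.0 point in 100 Stratum 2 subjects.

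Two larger conclusions might be inferred, and neither holds. One is that the primary result is at risk: primary ORR ignores scans after RECIST 1.1 PD, so it and its two tests are unaffected. The other is a head count, obtained by multiplying an assumed number of progressing subjects by an assumed share needing analgesia, radiation or palliative care. The documents give neither input, and the product would include subjects who fail a shared criterion and are unstable under both lists. The number affected is unknown.

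The outcome part of this conclusion assumes that the site continues and scans in one case and does not rescan in the other. The contradiction in treatment instructions needs no such assumption. This review takes no position on which list is clinically right.

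**What to change.** Reconcile Section 9.5.1.4.2 and Appendix 4 so that both carry one identical list of criteria, chosen by the sponsor. Check the chosen list against the radiation rule in Section 9.4.6.3, so that a permitted exception there does not conflict with the stability definition. Send sites a short clarification.

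The cost is one text alignment and one letter, with no new data. No sensitivity analysis is required: the affected outcomes are exploratory, scans after palliative radiotherapy are already excluded from irRECIST BOR, and the documents define no data item for increased analgesia at first PD. Concomitant therapy is recorded under Section 9.4.6, so the sponsor could attempt a descriptive listing, but that is optional.

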Appendix 5 New York Heart Association Cardiac Disease Classification

The New York Heart Association (NYHA) Cardiac Disease Classification provides a functional and therapeutic classification for the prescription of physical activity for cardiac subjects. On the basis of NYHA definitions, subjects are to be classified as follows:

Class	Definition
Class I	Subjects with no limitation of activities; they suffer no symptoms from ordinary activities.
Class II	Subjects with slight, mild limitation of activity; they are comfortable with rest or with mild exertion.
Class III	Subjects with marked limitation of activity; they are comfortable only at rest.
Class IV	Subjects who should be at complete rest, confined to bed or chair; any physical activity brings on discomfort and symptoms occur at rest.

Adapted from [The Criteria Committee of the New York Heart Association, 1994](#).

Appendix 6 Common Terminology for Adverse Events (version 4.03)

The National Cancer Institute's CTCAE v4.0 published 28 May 2009 (v4.03: June 14, 2010) provides descriptive terminology to be used for AE reporting in clinical studies. A brief definition is provided to clarify the meaning of each AE term. To increase the accuracy of AE reporting, all AE terms in CTCAE version 4.0 have been correlated with single-concept, MedDRA terms.

Grades in CTCAEs v4.03 refer to the severity of the AE. Grades of 1 through 5, with unique clinical descriptions of severity for each AE, are based on this general guideline:

Grade	Status
1	Mild: asymptomatic or mild symptoms; clinical or diagnostic observations only; intervention not indicated.
2	Moderate: minimal, local, or noninvasive intervention indicated; limiting age-appropriate instrumental ADL. ^a
3	Severe or medically significant but not immediately life-threatening: hospitalization or prolongation of hospitalization indicated; disabling, limiting self-care ADL. ^b
4	Life-threatening consequences: urgent intervention indicated.
5	Death related to adverse event.

ADL = Activities of Daily Living.

a: Instrumental ADL refers to preparing meals, shopping for groceries or clothes, using the telephone, managing money, etc.

b: Self-care ADL refers to bathing, dressing and undressing, feeding self, using the toilet, taking medications, and not bedridden.

Cancer Therapy Evaluation Program, NCI CTCAE v4.0. Available from:

http://ctep.cancer.gov/protocolDevelopment/electronic_applications/docs/ctcae4.pdf

For further details regarding MedDRA, refer to the MedDRA website at:

<http://www.meddramsso.com>. CTCAE v4.0 is available online at:

http://ctep.cancer.gov/protocolDevelopment/electronic_applications/docs/ctcae4.pdf.

Appendix 7 ECOG Performance Status Scale

Grade	ECOG Performance Status
0	Fully active, able to carry on all pre-disease performance without restriction.
1	Restricted in physically strenuous activity but ambulatory and able to carry out work of a light or sedentary nature (eg, light house work, office work).
2	Ambulatory and capable of all self-care, but unable to carry out any work activities. Up and about more than 50% of waking hours.
3	Capable of only limited self-care, confined to bed or chair more than 50% of waking hours.
4	Completely disabled. Cannot carry on any self-care. Totally confined to bed or chair.
5	Dead

ECOG = Eastern Cooperative Oncology Group.

Adapted from [Oken, et al., 1982](#).

Appendix 8 Breast Cancer TNM Staging System

Tumor (T), Node(N), Metastases (M)	
Stage	Thickness/Characteristics
T Classification	
TX	Primary tumor cannot be assessed
T0	No evidence of primary tumor
Tis	Carcinoma in situ; intraductal carcinoma, lobular carcinoma in situ or Paget's disease of the nipple with no associated tumor
T1	Tumor ≤ 2.0 cm in greatest dimension
T1mic	Microinvasion of ≤ 0.1 cm in greatest dimension
T1a	Tumor >0.1 cm, but ≤ 0.5 cm in greatest dimension
T1b	Tumor >0.5 cm, but ≤ 1.0 cm in greatest dimension
T1c	Tumor >1.0 cm, but ≤ 2.0 cm in greatest dimension
T2	Tumor >2.0 cm, but ≤ 5.0 cm in greatest dimension
T3	Tumor >5 cm in greatest dimension
T4	Tumor of any size with direct extension to (a) chest wall or (b) skin
T4a	Tumor of any size with direct extension to chest wall
T4b	Edema (including peau d'orange) or ulceration of the skin of the breast or satellite skin nodules confined to the same breast
T4c	Both Ta and Tb
T4d	Inflammatory carcinoma ^a
Regional Lymph Nodes (N) Classification	
NX	Regional lymph nodes cannot be assessed (eg, previously removed)
N0	No regional lymph node metastasis
N1	Metastases to movable ipsilateral level I, II axillary lymph node(s)
N2	Metastases to ipsilateral level I, II axillary lymph nodes that are clinically fixed or matted; or in clinically detected ipsilateral internal mammary nodes in the absence of clinically evident axillary lymph node metastases
N3	Metastases in ipsilateral infraclavicular (level III axillary) lymph nodes with or without level I, II axillary lymph node involvement; or in clinically detected ipsilateral internal mammary lymph node(s) with clinically evident level I, II axillary lymph node involvement; or metastases in ipsilateral supraclavicular lymph node(s) with or without axillary or internal mammary lymph node involvement
N3a	Metastases in ipsilateral infraclavicular lymph node(s)

Tumor (T), Node(N), Metastases (M)	
Stage	Thickness/Characteristics
N3b	Metastases in ipsilateral internal mammary lymph node(s) and axillary lymph node(s)
Pathologic (pN) Classification	
pNX	Regional lymph nodes cannot be assessed (not removed for pathologic study or previously removed)
pN0	No regional lymph node metastasis identified histologically
pN1	Micrometastases, or metastases in 1 to 3 axillary lymph nodes, and/or in internal mammary nodes with metastases detected by sentinel lymph node biopsy but not clinically detected
pN1a	Metastases in 1 to 3 axillary lymph nodes (at least one >2.0 mm)
pN1b	Metastasis in internal mammary lymph nodes with micro- or macrometastases detected by sentinel lymph node biopsy but not clinically detected
pN1c	Metastases in 1 to 3 axillary lymph nodes and in internal mammary lymph nodes with micro- or macrometastases detected by sentinel lymph node biopsy but not clinically detected
pN2	Metastases in 4 to 9 axillary lymph nodes or in clinically detected and in internal mammary lymph nodes in the absence of axillary lymph node metastases
pN2a	Metastases in 4 to 9 axillary lymph nodes (at least one tumor deposit >2.0 mm)
pN2b	Metastases in clinically detected internal mammary lymph nodes in the absence of axillary lymph node metastases
pN3	Metastases in 10 or more axillary lymph nodes or in infraclavicular (level III axillary) lymph nodes or in clinically detected ipsilateral internal mammary lymph nodes in the presence of 1 or more positive level I, II axillary lymph nodes; or in >3 axillary lymph nodes and in internal mammary lymph nodes with micro- or macrometastases detected by sentinel lymph node biopsy but not clinically detected; or in ipsilateral supraclavicular lymph nodes
pN3a	Metastases in 10 or more axillary lymph nodes (at least one tumor deposit >2.0 mm) or metastases to the infraclavicular (level III axillary) lymph nodes
pN3b	Metastases in clinically detected ipsilateral internal mammary lymph nodes in the presence of 1 or more positive axillary lymph nodes with micro- or macrometastases detected by sentinel lymph node biopsy but not clinically detected
pN3c	Metastases in ipsilateral supraclavicular lymph nodes
Distant Metastases (M) Classification	
MX	Presence of distant metastasis cannot be assessed
M0	No distant metastasis
M1	Distant metastasis present (includes metastasis to ipsilateral supraclavicular lymph nodes)

Clinical detection: as detected by imaging studies.

a: Inflammatory carcinoma is a clinicopathologic entity characterized by diffuse brawny induration of the skin of the breast with an erysipeloid edge, usually without an underlying palpable mass. Radiographically there may be a detectable mass and characteristic thickening of the skin over the breast. This clinical presentation is

due to tumor embolization of dermal lymphatics with engagement of superficial capillaries.
Available from <https://cancerstaging.org/references-tools/quickreferences/Pages/default.aspx>

